#### **Secondary Outcome Measures:**

**1**. To evaluate the safety and tolerability of CBD in PD:

1.1 By examining the frequency of study-related adverse events at each dose level between the two groups (treatment vs. placebo). Adverse events are measured at study visits, starting with an open ended question (Do you notice any effects, good or bad, of the study drug?) and followed by a series of yes/no questions regarding adverse effects (including previously reported adverse effects of CBD and general common adverse effects of medications and the hepatotoxicity), and all the effects we hypothesize in the study. For each adverse and beneficial reported effect, further questions will be asked, such as when did the effect start and how is it progressing, etc. In addition, since a major dose limiting effect is somnolence, the daytime sleepiness part of the SCOPA-sleep is included.

Tolerability is judged and supervised by PI and sub-I (who are MDs), based on their clinical expertise.

Abuse-related AEs will also be collected at screening, each dose assessment visit, liver function monitoring visit, and safety follow up visit. The abuse-related AEs is provided by MedDRA Preferred Terms (PTs), including:

Euphoria-related terms: Euphoric mood, elevated mood, feeling abnormal, feeling drunk, feeling of relaxation, dizziness, thinking abnormal, hallucination, inappropriate affect. Terms indicative of impaired attention, cognition, and mood: Somnolence, mood disorders, and disturbances.

Dissociative/psychotic terms: Psychosis, aggression, confusion, and disorientation. Related terms not captured elsewhere: Drug tolerance, habituation, drug withdrawal syndrome, substance-related disorders.

The Abuse-related AEs will be collected and recorded on a CRF that includes timing of the event, duration, severity, indication if more than one event was observed simultaneously, if other drugs were taken by subjects at the time of the event, correlation between the onset of the event, and the use of study drug.

Well trained investigators will capture and report cases of abuse, misuse, or addiction and monitor for drug accountability discrepancies before starting trials.

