## Assessment of tolerability of each dose level

Tolerability will be assessed at each dose via collection of adverse events and administration of the standardized questionnaires by appropriate study staff during each clinic visit. Severity of adverse events will be graded according to the Common Terminology Criteria for Adverse Events (CTCAE), which is published by the National Cancer Institute (NCI) of the National Institutes of Health (NIH): Grade 1: Mild; asymptomatic or mild symptoms; clinical or diagnostic observations only; intervention not indicated.

Grade 2: Moderate; minimal, local, or noninvasive intervention indicated; limiting age-appropriate instrumental ADLs. Instrumental ADLs refer to preparing meals, shopping for groceries or clothes, using the telephone, managing money, etc.

Grade 3: Severe or medically significant but not immediately life-threatening; hospitalization or prolongation of hospitalization indicated; disabling; limiting self-care ADLs. Self-care ADLs refer to bathing, dressing and undressing, feeding self, using the toilet, taking medications, and not bedridden.

Grade 4: Life-threatening consequences; urgent intervention indicated.

Grade 5: Death related to AE.

The protocol for dose adjustments, maintenance, and discontinuation based on adverse effects is as follows:

- For participants with a grade 1 adverse event the dose will be increased by up to 1.25 mg/kg/day, or if they are on the maximal targeted dose (2.5 mg/kg/day) it will be continued.
- For participants with a grade 2 adverse event the dose will be reduced by 1.25 mg/kg/day or less.
- For participants with a grade 3 or 4 adverse event that the Investigator determines is unrelated, the dose will be continued. When the adverse event is stabilized or resolved, e.g., participant is stable after a hip fracture repair, the dose will be increased unless they are already on the maximum targeted dose.
- For participants with a grade 3 or 4 adverse event that the Investigator determines is related the study drug will be stopped and not restarted.

The Investigator will determine relatedness as described in Section IV. C.6, and will consider the adverse event related if she determines there is at least a reasonable possibility.

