#### C.2 Study Drug: CBD:

The study drug is supplied by NIDA; see Appendix 4 for Certificate of Analysis (COA). The study drug (CBD) is provided in the form of a thick liquid and will be diluted into a 100 mg/ml formulation with sesame oil. This procedure will be done by the PharmDs ([name], [name], and [name] as a consultant) or PI, according to the protocol we develop with guidance from NIDA and the University of Mississippi researchers that produced the material. The placebo will be made by the study Pharm Ds from USP grade sesame oil and food coloring. Because the placebo may be slightly different in appearance or taste, two study modifications are being done to preserve the blind. First, the study drug will be put into brown opaque bottles and the only study personnel to see the actual study drug will be the unblinded PharmD and the blinded CTRC PA that instructs the subject on how to take study drug. Further, the study drug is administered in a closed, vented room in the CTRC that removes the odor of cannabis within four minutes. After the study drug is administered and the study drug bottle closed, the PA will stay with the subject in the closed room while it is being vented for at least 10 minutes. The study design of parallel groups is being used instead of the original crossover design that was planned.

ElSohy Laboratories, Incorporated (ELI) will perform the stability testing. The laboratory is registered with the FDA and the DEA (Manufacturing and Analytical), all the planned analytical

procedures are validated, and the lab has extensive experience with the drug substance (CBD extract) and with a very similar drug product to ours. Controls for both CBD and THC content are used. The stability testing will be done in real time.

The shelf life will be determined by the testing described below. The final drug product will be stored at room temperature, 25°C.

The microbial testing for the final drug product will be carried out according to UPS 61 (total aerobic microbial count and total combined yeast/mold count) and USP 62 (for salmonella and E. coli), and the specification and acceptance criteria will be the same as recommended in USP <111> (microbiological examination of non-sterile products: Acceptance Criteria for Pharmaceutical Preparations and Substances for Pharmaceutical Use for non-sterile, non-aqueous products with oral administration). This will be the same for the product and placebo. Microbial Specifications:

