Adverse events will be considered "related" to the use of the study drug if none of the "not related" criteria are met. The Investigator will use clinical judgment to determine the relationship of the AE/SAE to study drug. An AE/SAE may be related to the study drug, other concomitant medications, intercurrent illness, a procedure performed in the course of the study, or another reason. Among the potential etiologies, the Investigator will make a determination based on the most likely causal relationship. Alternative causes, such as the natural history of any underlying diseases, concomitant therapy, other risk factors, and the temporal relationship of the event to the study drug will be considered. The Investigator will also take into account the Investigator's Brochure in the causality assessment. There may be situations when an SAE has occurred and the Investigator will make an assessment of causality prior to transmission of the SAE report to the Sponsor, as the causality assessment is one of the criteria used when determining regulatory reporting requirements. The Investigator may change the causality assessment in light of follow-up information by amending the SAE report accordingly.

SAEs that are considered related (i.e., determined to be possibly, probably, or definitely related) to the investigational product by the Sponsor-Investigator will be followed until the event resolves or stabilizes. Any SAE that occurs after treatment completion, and is considered by the Sponsor-Investigator to be related to the investigational product, will be documented and reported as appropriate.

Reporting Serious Adverse Events to Regulatory Agencies

Events meeting the following criteria will be submitted to the Food and Drug Administration (FDA) as expedited IND Safety Reports according to the following guidance and timelines: 7 Calendar Day Telephone or Fax Report

The Sponsor-Investigator will notify the appropriate review division at the FDA of any fatal or lifethreatening adverse event that is unexpected and assessed by the Sponsor-Investigator to be possibly related to the use of the investigational product. An unexpected adverse event is one that is not already described in the investigational product's Investigator Brochure. Such reports are to be telephoned or faxed to the appropriate review division at FDA and to the manufacturer of the investigational product within seven calendar days of first learning of the event.

15 Calendar Day Written Report

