- 4. Adverse events and serious adverse events will be reported from the time of study drug administration until the last study visit or death, whichever occurs first, according to mandated guidelines.
- 5. All adverse events and serious adverse events will be followed until resolution (or return to baseline status), or until the condition stabilizes or is otherwise explained, or until participant dies or is lost to follow-up.
- 6. Safety assessments are comprehensive and include vital signs, history and physical examination, concomitant medications collection, EKGs, safety labs (Hematology, Hemoglobin A1C, Complete Metabolic Profile and Liver Function Tests), blood and urinary cannabis and metabolites analysis, MoCA, QUIP-RS, C-SSRS, NPI, SCOPA-sleep, Anxiety short form, Depression short form, Emotional and behavioral dyscontrol short form, Fatigue Severity Scale, Pain Intensity and Interference short form, study drug compliance check, adverse event check, and urine and blood pregnancy testing.

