#### F. Data Analysis Plan:

Intention to treat concept is followed. In order to minimize data entry errors a double data entry system will be used.

If study participant agrees, the de-identified data would be shared within CDPHE Marijuana grantee consortium for future research.

The analysis will be performed in accordance with the analysis plan devised prior to unblinding. Baseline variables will be examined for equality between the two sequence groups. The primary, secondary and exploratory outcomes will be analyzed as below from baseline to the end of 2.5 mg/kg/day.

Primary Specific Aim: To evaluate the efficacy of CBD on motor symptoms in PD. The data will be analyzed to compare two randomized independent samples, CBD and placebo. Means and confidence intervals will be presented for the pre and post outcome values by treatment, and for the change scores between pre and post treatment within treatment group. A two independent sample T-test will compare the means of the change scores between the treatment groups. We will test the null hypothesis of no treatment effect. Longitudinal regression models will be fit for further analysis, including adjusting for covariates if necessary.

Secondary Specific Aim is to examine safety and tolerability of CBD and the effect of CBD on severity and duration of intractable tremor and other symptoms in PD.

Safety and tolerability and will be assessed in five ways:

- Frequency of study-related adverse events at each dose level collected at study visits. Analysis (frequency of study-related adverse events at each dose level in the two groups, treatment vs. placebo) will be mostly descriptive and proportions and confidence intervals will be calculated. Contrasts involving repeated measures on the same participants can be tested with McNemar's test (for two correlated proportions) or GEE models/GLMMs. Contrasts for independent data can be tested with standard two sample proportions test and with GLMs. Proportions, logistic regression, and relative risk regression can be applied to binary outcomes over a fixed period of time, and Poisson models can be applied to counts or events over time.

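### The only adverse-event comparison between arms counts study-related events, so it rests on investigator attribution; comparing all treatment-emergent events is a cheap improvement.

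*Combined protocol and SAP*

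**What the plan says.** Section IV.A, Secondary Outcome Measures 1.1, assesses safety "By examining the frequency of study-related adverse events at each dose level between the two groups". Section IV.F gives the matching analysis as "frequency of study-related adverse events at each dose level in the two groups, treatment vs. placebo", with proportions and confidence intervals. It calls this mostly descriptive and names tests only as options. The term study-related is not defined; Section IV.C.6 defines relatedness to study drug.

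Collection is not restricted. Section IV.D states that "Adverse events and serious adverse events will be reported from the time of study drug administration until the last study visit or death", and that all events are followed to resolution or stabilisation.

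On attribution, C.6 first makes an event related by default, unless one of three exclusion criteria is met. The third criterion requires an alternative explanation that is clearly more likely. C.6 then says that, among potential causes, "the Investigator will make a determination based on the most likely causal relationship". Section IV.C.1, on tolerability at each dose level, refers to C.6 and adds that the investigator "will consider the adverse event related if she determines there is at least a reasonable possibility".

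On blinding, Section IV.C.2 introduces its safeguards with "Because the placebo may be slightly different in appearance or taste". Section IV.C.4 puts the blinding questionnaire to participants only.

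**The concern.** With a placebo arm, the difference in all events between arms estimates the drug effect, and background events are expected equally in both. Restricting the count to events judged related applies a post-randomisation judgement to each event before the arms are compared. Two things can follow.

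- If attribution differs by arm, for instance because taste, appearance or smell hints at the allocation, a difference can appear where none exists, or a real one can shrink.
- If attribution is the same in both arms but incomplete, a real difference in risk shrinks. Somnolence and fatigue, the effects most often reported in the open-label study, overlap with problems that PD itself causes, so an alternative explanation will often be available.

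Safety and tolerability form part of the secondary aim and Hypothesis 2, so this count will be read as a main safety result.

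**Working it through.** **1. Do the attribution wordings agree?** Take an event for which another cause is more likely than the drug, but not clearly so, and no other exclusion criterion applies.

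| Wording | Where | Classification |
|---|---|---|
| Related unless an exclusion criterion is met | C.6 | Related |
| Most likely cause | C.6 | Not related |
| At least a reasonable possibility | C.1, referring to C.6 | Related, if the drug remains a reasonable possibility |

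The firm conflict is between the two rules inside C.6. The C.1 wording can be read as a paraphrase of C.6, but it does not settle which rule applies. C.6 also speaks of serious events as possibly, probably or definitely related, after setting a two-category scale.

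**2. Numbers per arm.** The plan gives no figure for the adverse-event comparison. Its sample size for the primary endpoint reproduces: 5.75/6.72 = 0.856. A two-sided two-sample t-test at 0.05 needs 22.44 per arm for 80% power and 29.70 for 90%, so 46 and 60 in total. Dividing by 0.8 gives 58 and 75. I therefore use 30 per arm (completers) and 37 per arm (recruited, 75/2 rounded down).

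**3. Attribution that differs by arm (assumed rates).** The true risk of an event, p, is the same in both arms. A participant with an event is counted as related with probability a1 on CBD and a0 on placebo, so the observed risks are p×a1 and p×a0. The pooled test rejects when |x1 − x0|/n divided by √(p̄(1 − p̄)×2/n) exceeds 1.96. Here x1 and x0 are the related counts in the two arms and p̄ = (x1 + x0)/(2n). The exact binomial probabilities of all rejecting outcomes are summed.

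| p | a1 / a0 | Observed risks | Rejects, n=30 | Rejects, n=37 |
|---|---|---|---|---|
| 50% | 70% / 70% | 35% v 35% | 4.8% | 4.9% |
| 50% | 80% / 60% | 40% v 30% | 12.3% | 14.3% |
| 50% | 80% / 50% | 40% v 25% | 23.0% | 28.0% |
| 30% | 80% / 50% | 24% v 15% | 13.8% | 16.2% |
| 70% | 80% / 50% | 56% v 35% | 37.9% | 43.6% |

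At p = 50% the apparent risk ratios are 40/30 = 1.33 and 40/25 = 1.6, with no true difference.

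**4. Equal but incomplete attribution (assumed rates).** Use the somnolence rates in Table 7, which come from a different population and dose: 22/61 = 36.1% against 6/59 = 10.2%, a difference of 25.9 points. If 70% of events in each arm are called related, the difference is 0.7 × 25.9 = 18.1 points; at 50% it is 12.9 points. Power at 30 per arm goes from 69% on all events to 50% and then 37%.

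**The case against.** A reader might infer that the whole safety comparison is filtered by relatedness. The documents do not support that. Section IV.F announces five safety assessments and lists four, and related events are only the first. Vital signs, laboratory values and the standardized scales are compared between arms without attribution, and these include a daytime-sleepiness scale for the main dose-limiting effect. Dropout for intolerance is also compared, though it rests on a judged cause. These comparisons do not replace an event count: in the open-label study participants often reported somnolence and fatigue while the formal tools showed no change.

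A reader might also infer that attribution is already biased, or that three independent rules compete. Neither is shown. The protocol says only that the placebo may differ slightly. It provides opaque bottles and a vented dosing room, and it keeps the investigator nominally blinded. The C.1 wording defers to C.6. The default-related rule also leans towards keeping events in the count.

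The comparison is secondary and mostly descriptive, so a rejection rate is a yardstick for distortion, not a planned error rate. Sound attribution can also remove background noise, which is a reason to keep a related-events table. Finally, comparing all events does not cure an imperfect blind, because participants' own reporting may still differ by arm. It does remove the investigator's filter.

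**Conclusion.** The point holds for the adverse-event comparison alone. The plan specifies no comparison of all events by arm, although the data will exist, and the comparison it does specify depends on attribution under two C.6 rules that can disagree. Differential attribution is a risk that the documents leave open and would have little means of detecting, because only participants are asked to guess the allocation. It is not a demonstrated bias.

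The 12-23% rejection at 30 per arm (14-28% at 37) rests on assumed attribution of 80% against 50-60%, a true risk of 50% in both arms and one yes/no outcome per participant. None of these rates comes from the documents. With equal attribution the rate stays near 5%. This is a cheap improvement, and no conclusion on the primary endpoint depends on it.

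**What to change.** - In outcome 1.1 and Section IV.F, make all treatment-emergent adverse events, whatever their attribution, the between-arm comparison. Give the proportion of participants per arm and the difference with a 95% confidence interval, by dose period and overall.
- Show events judged related as a supporting table, and replace the undefined term study-related with related to study drug.
- Reconcile the relatedness wordings in C.1 and C.6. They also feed the dose-adjustment and stopping provisions in C.1 and C.5. No view is taken here on which wording is right.

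The cost is one extra table and higher reported event counts in both arms. No new data are needed, and the targets of 60 completers and 75 recruited stay as they are.

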# Impulsivity:

• Impulsive-Compulsive Disorders in Parkinson's Disease-Rating Scale (QUIP-RS) is a rating scale designed to measure severity of symptoms and support a diagnosis of impulse control disorders and related disorders in PD. QUIP-RS has four primary questions (pertaining to commonly reported thoughts, urges/desires, and behaviors associated with ICDs), each applied to the four ICDs (compulsive gambling, buying, eating, and sexual behavior) and three related disorders (medication use, punding, and hobbyism). It uses a five-point Likert scale (score 0-4 for each question) to gauge the frequency of behaviors, and instructs patients to answer questions based on behaviors that occurred in the preceding four weeks (or any four-week period in a designated time frame). Scores for each ICD and related disorder range from 0 to 16, with a higher score indicating greater severity (ie, frequency) of symptoms. The total QUIP-RS score for all ICDs and related disorders combined ranges from 0 to 112 [Weintraub D, et al. 2012].

Suicidality:

• The Columbia-Suicide Severity Rating Scale (C-SSRS) is a suicidal ideation rating scale. It rates an individual's degree of suicidal ideation on a scale, ranging from "wish to be dead" to "active suicidal ideation with specific plan and intent." The scale identifies behaviors which may be indicative of an individual's intent to commit suicide. The C-SSRS has been found to be reliable and valid in the identification of suicide risk in several research studies.

Motor and non-motor PD signs:

Movement Disorder Society Unified Parkinson Disease Rating Scale (MDS-UPDRS)-The MDS UPDRS has four parts: Part I (non-motor experiences of daily living), Part II (motor experiences of daily living), Part III (motor examination) and Part IV (motor complications). Part I has two components: IA concerning a number of behaviors that are assessed by the investigator with all pertinent information from patients and caregivers and IB that is completed by the patient with or without the aid of the caregiver, but independently of the investigator. It can, however, be reviewed by the rater to ensure that all questions are answered clearly and the rater can help explain any perceived ambiguities. Part II is designed to be a self-administered questionnaire like Part IB, but can be reviewed by the investigator to ensure completeness and clarity. Part III has instructions for the rater to give or demonstrate to the patient; it is completed by the rater. Part IV has instructions for the rater and also instructions to be read to the patient. This part integrates patient-derived information with the rater's clinical observations and judgments and is completed by the rater.

- Unified Dyskinesia Rating Scale (UDysRS) is developed to evaluate involuntary
  movements often associated with treated Parkinson's disease. There are two primary
  sections: Historical [Part 1 (On-Dyskinesia) and Part 2 (Off-Dystonia)] and Objective
  [Part 3 (Impairment) and Part 4 (Disability)]. On-Dyskinesia refers to the choreic and
  dystonic movements described to the patient as "jerking or twisting movements that occur
  when your medicine is working." Off-Dystonia should be described to the patient as
  "spasms or cramps that can be painful and occur when your Parkinson's disease
  medications are not taken or are not working."
- Timed Up&Go (TUG) test: The TUG test is a validated, widely used test for evaluating balance and walking ability associated with advancing age, neurological (especially PD), or other disorders [Bohannon RW, et al. 2006].
- Non-motor symptoms Scale for Parkinson's disease (NMSS): NMSS is a validated 30item scale for the assessment of NMS in PD. NMSSS contains nine dimensions: cardiovascular, sleep/fatigue, mood/cognition, perceptual problems, attention/memory, gastrointestinal, urinary, sexual function, and miscellany.

Restless Legs Syndrome:

International Restless Legs Syndrome Study Group Rating Scale for restless legs syndrome (IRLS): IRLS is a ten-question instrument for measuring severity of restless legs syndrome (RLS). The scale reflects participants assessment of the primary features (reflected in questions 1 through 3 and 6 of the scale), intensity and frequency of the disorder (questions 7 and 8 of the scale) and associated sleep problems (reflected in questions 4 and 5 of the scale). The scale also includes questions which probe the impact of symptoms on the patients' mood and daily functioning (question 9 and 10 of the scale). Each question has a set of five response options graded from no RLS or impact (score=0) to very severe RLS or impact (score=4). This produced a total scale whose overall score could range from 0 to 40. IRLS sum score and subscales (symptoms in questions 1, 2, 4, and 6 through 8; symptoms impact in questions 5, 9, and 10) at every time point will be recorded. Item 3 is used for the total score for overall RLS severity.

